##### **3.1.2 Subject Disposition and Discontinuation from Study**

The number of subjects screened, randomized and treated will be presented together with the study completion status and the reasons for discontinuation grouped by treatment and by major reason (lost to follow-up, adverse event, poor compliance etc.).

A listing will be provided of all patients discontinued from the study after enrolment, broken down by center and treatment group, giving a patient identifier, the specific reason for discontinuation, the treatment (drug and dose), and the duration of treatment before discontinuation. Whether or not the blind for the patient was broken at the time of discontinuation will be noted. Demographic and Baseline Characteristics  
Demographic and baseline characteristics will be presented in the data listings.

Descriptive summary statistics (n, mean, standard deviation, median, minimum, and maximum) and/or frequency distributions, as appropriate, will be generated by randomized treatment group and combined.

### **3.1.3 Wart Diagnosis and Characteristics at Baseline**

Descriptive summary statistics (n, mean, standard deviation, median, minimum, and maximum) and/or frequency distributions, as appropriate, will be generated by randomized treatment group and combined. Summarized variables include total warts treated, time since first appearance of most and least recent treated warts, longest axis of largest wart treated, and thickness of largest wart treated.

### **3.1.4 Prior and Concomitant Medications, Therapies and Procedures**

Medications are coded using the WHO Drug (March 2019). Prior and concomitant medications are listed only. The period(s) in which the medications were administered will be flagged.

### **3.1.5 Protocol Violations**

[figure not shown]
Protocol violations will be identified prior to database lock to measure adherence to key aspects the protocol (see section 16.2 of the protocol for full definitions). Specific data fields that will be examined to identify protocol violations include entrance inclusion/exclusion criteria and prohibited prior and concomitant medications as well as all deviations identified by the investigator. All protocol violations will be listed by patient number and summarized (n and percent) by randomized treatment group.

## **3.2 Efficacy Endpoints**

The primary efficacy analysis will evaluate the effectiveness of A-101 45% compared to Vehicle at the endpoint visit, Visit 10 (Day 60). It will be based on the proportion of subjects who achieve complete clearance (PWA=0) of all treated common warts.

Four secondary efficacy analyses will be performed and tested in a hierarchical Fixed-Sequence step-down method to control alpha among the pre-specified secondary efficacy variables. The predefined order of the tests is specified to be the order of these analyses as presented below (Figure 1). All analyses will be conducted at the same alpha level (2-tail alpha = 0.05). The results of the second analysis will only be reported if the first analysis reaches statistical significance at alpha = 0.05. The results of the third analysis will only be reported if the first and second analyses reach statistical significance, each at alpha = 0.05. The results of the fourth analysis will only be reported if the first, second and third analyses reach statistical significance, each at alpha = 0.05.

**Figure 1 Hierarchical Testing of Primary and Secondary Endpoints to Maintain Study-Wise Type I error at  $\alpha=0.05$  (2-Sided)**

For regulatory purposes, testing will halt at the first endpoint with  $P > 0.05$ , however all endpoints will be analyzed irrespective of the results. Supportive and sensitivity analyses of the primary and secondary endpoints will also be performed.

Should sparse enrollment at one or more sites occur, the following algorithm will be employed to “pool” sites for analysis. Sites with fewer than 5 subjects randomized will be pooled by ordering the sites based on the number of subjects randomized and the site number (in the event multiple sites have the same number randomized) and then combining the smallest with the next smallest site in the sort order in a stepwise fashion until all the sites/pooled sites have more than 4 subjects. A pooled site can be pooled again if, after an initial pooling, it remained part of the smallest or next smallest site or pooled site. In the sort order when there are ties in count, a “pooled site” comes after non-pooled sites in the pooling hierarchy. The pooled site(s) will be used in all analyses that are stratified by site and/or include site in the statistical model.

### 3.2.1 Complete Clearance of All Warts

The primary efficacy analysis will evaluate the effectiveness of A-101 45% compared to Vehicle at the endpoint visit, Visit 10 (Day 60). It will be based on the proportion of subjects who achieve complete clearance (PWA=0) of all treated common warts. A

Cochran-Mantel-Haenszel (CMH) test stratified by the baseline number of treated warts (1 wart, 2 warts, 3 warts, >3 warts) will be used to perform the primary efficacy comparison between treatment groups, with 2-tail alpha set at 0.05. Any treated common wart for a randomized subject that has missing data at the endpoint visit will be treated as not clear for the purpose of the primary efficacy analysis. Corresponding estimates of the common Mantel-Haenszel odds ratio will be provided along with 95% confidence intervals (CIs). Stratum specific odds ratio estimates and 95% confidence intervals will also be provided.

Syntax for the SAS statements used to perform the analysis will be consistent with respect to the statistics calculated in the following:

```
PROC FREQ;  
TABLE WARTS*TREATMENT*RESPONSE/CMH;  
OUTPUT OUT=STATS (KEEP=P_CMHGA _MHOR_ L_MHOR U_MHOR P_BDCHI) CMH;
```

Where WARTS represents the number of warts assessed at baseline (1 wart, 2 warts, 3 warts, >3 warts); TREATMENT is 1 for A-101 and 2 for Vehicle; and RESPONSE = 1 for those with all warts cleared and 2 for those without all warts cleared. P\_CMHGA is the CMH general association test, \_MHOR\_ is the Mantel-Haenszel estimated common odds ratio, and L\_MHOR and U\_MHOR are the lower and upper limits, respectively, of the corresponding 95% confidence interval. P\_BDCHI is the p-value from the Breslow-Day test of the homogeneity of the odds ratios across strata and is provided as a supportive statistic to assess the model. A statistically significant finding (P<0.05) of the Breslow-Day test indicates that the treatment effect differs by stratum and these differences should be investigated by stratum-specific odds ratios estimates which will be included in the output for the primary endpoint.

### 3.2.2 Sensitivity Analyses for the Primary Endpoint

The first sensitivity analysis for the primary endpoint will be an analysis based upon the PP population. This analysis will use the same CMH model described for the primary analysis.

A second sensitivity analysis will be conducted for the primary endpoint using the same CMH model for the ITT population that includes the imputation of missing PWA data using a fully conditionally specified (FCS) regression-based Multiple Imputation (MI) procedure. This regression-based MI will be conducted on the worst (maximum) PWA score for all treated warts at a given visit for each subject. The utilization of the FCS methodology accounts for the correlation within a subject and models mean changes over time in the maximum PWA score. For each subject, only data selected as representative of an analysis visit (i.e. within the defined relative day range and closest to the “target”) as documented in Appendix B are included in the imputation process. The imputed data will be in the form of the maximum PWA score and will be rounded to an integer and bounded by 0 below and 3 above. All imputed maximum PWA scores that are assigned a 0 will correspond to complete clearance of all warts at that visit. The complete clearance at visit 10 using this MI data will be analyzed using the same CMH model described for

the primary analysis. Results from the CMH on the MI data will then be summarized using the Wilson-Hilferty transformation to obtain the sensitivity results primary efficacy endpoint. The SAS syntax used to perform the MI and the MI summary is shown in Appendix A

To assess the impact of missing data imputation on primary analysis results a tipping point analysis will be conducted. This analysis will shift the treatment coefficient in the regression model used in the MI procedure to impose a worse mean maximum PWA for the A-101 45% arm and a better mean maximum PWA for the vehicle arm. The shifts will be from 0 to 3 in increments of 0.5 for the A-101 45% arm and from 0 to -3 in increments of 0.5 for the vehicle arm. Apart from these tipping point shifts, the analysis will follow the same methodology described for the MI procedure. The odds ratio and CMH Chi-square P-value are provided for each of the  $7 \times 7 = 49$  shift combinations for the two arms.

In addition, a model similar to the primary analysis model but stratified instead by Study Center will be performed as a sensitivity analysis including the Breslow-Day test to evaluate heterogeneity across sites. The SAS syntax differs only by replacing the WARTS in the above example with SITE where site may be a “pooled site” as detailed in section 3.2.

### **3.2.3 Secondary Efficacy Endpoints**

Visit 13 (Day 137) will be analyzed using an identical model as the primary endpoint at Visit 10 (Day 60). This will be the first secondary endpoint tested in the hierarchy of endpoints described in Section 3.2. This analysis will be run on the ITT population using randomized treatment group.

Sensitivity analyses performed for the primary endpoint will be repeated for the Visit 13 analysis. These sensitivity analyses will include the PP analysis, missing data imputation impact analyses, and the tipping point analysis. The site heterogeneity analysis will not be performed.

### **3.2.4 Mean Per Subject Percent of Warts Cleared**

Mean per-subject percent of warts cleared at Visit 13 (Day 137) will be evaluated as the second secondary endpoint using analysis of covariance (ANCOVA) with treatment group as a class variable and the baseline number of warts assessed as a continuous covariate. Patients without a week Visit 13 measurement according to the assignment to analysis visit in Appendix B will be assigned a score of 0% warts cleared. Ninety-five percent confidence intervals will be constructed about the estimated treatment difference based on the model estimates and associated variability.

Syntax for the SAS statements used to perform the analysis will be consistent with respect to the statistics calculated in the following:

PROC GLM;  
CLASS TREATMENT;

```
MODEL PER_CLEAR = TREATMENT WARTS / SOLUTION CLPARM;  
LSMEANS TREATMENT / PDIFF STDERR ALPHA=0.05 CL E;  
ESTIMATE 'A-101 vs Vehicle' TREATMENT 1 -1 / CL;
```

Where WARTS represents the number of warts assessed at baseline; TREATMENT is 1 for A-101 and 2 for Vehicle; and PER\_CLEAR is the mean per subject percent of warts cleared.

A separate sensitivity analysis for the mean per-subject percent of warts cleared will be conducted using the PP population.

### 3.2.5 Complete Clearance in Subjects with a Single Wart at Baseline

A Cochran Mantel Haenszel (CMH) test stratified by investigative site will be used to compare treatment groups with respect to the proportion whose wart is Clear (PWA=0) at Visit 10 in the subset of ITT subjects with a single wart at baseline. This is the third secondary endpoint in hierarchy summarized in section 3.2.

Syntax for the SAS statements used to perform the analysis will be consistent with respect to the statistics calculated to the following:

```
PROC FREQ;  
TABLE SITE*TREATMENT*RESPONSE/CMH;  
OUTPUT OUT=STATS (KEEP=P_CMHGA_MHOR_L_MHOR_U_MHOR P_BDCHI) CMH;
```

Where SITE may be a “pooled site” as detailed in Section 3.2 and the other terms are as detailed in Section 3.2.1.

A sensitivity analysis for the complete clearance in subjects with a single wart at baseline will be conducted in the subset of the PP subjects with a single wart at baseline.

### 3.2.6 Time to Clearance of All Warts

The fourth secondary endpoint tested, the difference in time to clearance of all warts from randomization between the two treatment arms, is assessed in the ITT population using the stratified log-rank test (Score statistic from PHREG and ties=Breslow) from a Cox proportional hazards (CPH) model including treatment and the number of warts assessed at baseline in the model. Survival for each arm is summarized using Kaplan Meier curves and is further characterized in terms of the median and survival probability at selected timepoints, along with the corresponding 2-sided 95% confidence intervals for the estimates. Confidence intervals for median survival are based upon the methods of Brookmeyer and Crowley. Confidence intervals for survivorship estimates are calculated using the log-log transformation.

Syntax for the SAS statements used to perform the analysis will be consistent with respect to the statistics calculated to the following:

```
PROC PHREG;  
MODEL DAYSFOL*RESPONSE(2) = TREATMENT / RISKLIMITS TIES=BRESLOW;
```

STRATA WARTS;

Where WARTS represents the number of warts assessed at baseline (1 wart, 2 warts, 3 warts, >3 warts); TREATMENT is 1 for A-101 and 0 for Vehicle; and RESPONSE = 1 for those with all warts cleared and 2 for those without all warts cleared. Subjects without complete clearance (i.e. RESPONSE = 2) are censored on the date of the last wart assessment. DAYSFOL = Date of last wart(s) assessment – date randomized +1. Patients without a post baseline assessment are censored on date of randomization. The Wald Chi-Square P-value is used.

Kaplan-Meier estimates for plotting and for estimates of median and of the survivorship curve at selected times (Days from Randomization) will be obtained using SAS statements consistent with the following syntax:

```
PROC LIFETEST ALPHA=.05;  
TIME DAYSFOL*RESPONSE(2);  
SURVIVAL OUT=SURV CONFTYPE=LOGLOG;  
STRATA TREATMENT;
```

A sensitivity analysis for the time to clearance of all warts will be conducted on the PP population.

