#### **6.1.2. Secondary Objectives**

The secondary objectives of this study include:

- Duration of response to A-101 45% compared to Vehicle.
- Onset of action of A-101 45% compared to Vehicle.
- Safety of A-101 45%.

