### **12.3. Physician's Wart Assessment (PWA)**

The Physician's Wart Assessment (PWA) is the Investigator's assessment of the severity of each identified common wart at a particular time point. The Investigator should NOT refer to any other assessments to assist with this evaluation. This evaluation IS NOT a comparison with the PWA performed at any other visit.

At every study visit, the Investigator will assess each identified common wart and report the one integer that best describes the common wart severity using the following scale. At any visit where a study medication treatment is performed, the PWA must be completed prior to the treatment visit.

| Physician's Wart Assessment |   |
|------------------------------------|---|
| Grade                       | Descriptor   |
| 0                           | Clear: No visible wart. No further treatment is indicated                         |
| 1                           | Near Clear: a visible wart that is less than 3 mm in maximal diameter (or length) |
| 2                           | A visible wart $\geq$ 3 mm and $<$ 6 mm in maximal diameter (or length)           |
| 3                           | A visible wart $\geq$ 6 mm in maximal diameter (or length)                        |

The physician is encouraged to use a ruler or caliper and to feel the wart or skin area to help his/her assessment.

At Visit 1 for the subject to be enrolled and at Visit 2 for the subject to be randomized each identified wart must have a PWA grade  $\geq$  2.

At Visits 3-9, identified common warts must have a PWA  $> 0$  to be retreated. If the Investigator cannot assess the PWA for a common wart (e.g., the common wart cannot be visualized because of an LSR such as edema, scabbing, etc.) she/he must report the reason in the subject's CRFs. The identified common wart must not be retreated at that visit, and the subject should be seen at the next scheduled visit. All at home treatment visits will be based on the PWA score during the in-office visit.

Refer to [Appendix 2](#) for the PWA Site Manual.

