The fourth secondary efficacy analysis will a comparison between A-101 45% and Vehicle s with respect to the median time to achieve onset of Clearance (PWA=0) for all treated warts. It will be conducted as a comparison of median time for a subject to first achieve Clearance (PWA=0) of all treated warts, using a log rank test with 2-tail alpha set at 0.05. This will be a Kaplan-Meier time-to-event analysis providing standard survivor functions and comparisons of time-to-event curves using the log rank test, where time-to-event curves will be compared with two-tail alpha = 0.05, and median time to event will be presented for each treatment group. For each subject the time to achieve onset of complete treated wart Clearance will be calculated from the date of randomization to the earliest visit date when all treated warts are clear. In the event a subject does not attain complete wart Clearance, that subject's time-to-event data will be treated as censored for the Kaplan-Meier analysis.

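### The SAP's only time variable for time to clearance ends at the last wart assessment, not at the first all-clear visit that the protocol specifies, so the onset endpoint loses its onset information if coded as written

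*SAP*

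**What the plan says.** Protocol section 15.3 makes time to clearance of all treated warts the fourth secondary analysis, tested by log-rank at two-sided 0.05. Each subject's time is "calculated from the date of randomization to the earliest visit date when all treated warts are clear", and subjects who never clear are censored. The related secondary objective in protocol section 6.1.2 is "Onset of action of A-101 45% compared to Vehicle".

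SAP section 3.2.6 describes the same endpoint, but the only time variable it defines is "DAYSFOL = Date of last wart(s) assessment" minus the randomization date plus one. The event indicator is "RESPONSE = 1 for those with all warts cleared and 2 for those without all warts cleared". The PROC PHREG model uses this pair, and so does PROC LIFETEST, whose time statement begins "TIME DAYSFOL*RESPONSE(2". The section gives no date of first clearance.

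The section also names two test statistics. It opens with a "stratified log-rank test (Score statistic from PHREG and ties=Breslow" and later states "The Wald Chi-Square P-value is used".

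Protocol section 12.3 keeps the assessments going after clearance: "At every study visit, the Investigator will assess each identified common wart". The last is at Visit 13, Day 137, with a window of +7 days (protocol Table 2).

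**The concern.** The two documents end the clock at different visits. For a subject who clears before Visit 13 and completes the study, the SAP formula returns the end of follow-up instead of the onset of clearance. SAP section 3.6, which lists departures from the protocol, does not mention this.

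This is the last test in the fixed sequence and the only tested endpoint that measures when clearance begins. Under the literal formula the Kaplan-Meier curves stay near zero clearance until Visit 13, the medians stop describing onset, and the hazard ratio mostly compares the proportions who ever clear. The subgroup hazard ratios in SAP section 3.2.7 would inherit the problem.

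RESPONSE = 1 also has no time frame in section 3.2.6. It could mean clear at any visit or clear at the last assessment, and these differ when a wart recurs.

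**Working it through.** **Inputs from the documents.** About 500 subjects, 1:1; two-sided alpha 0.05; visits at Days 8, 15, 22, 29, 36, 43, 50, 60, 78, 106 and 137 with the Table 2 windows; four wart-count strata (1, 2, 3, >3). The power figures in protocol section 15.1 (above 90%, and 97% by simulation) concern the primary endpoint. None is given for time to clearance, so there is no stated figure to reproduce.

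**Date arithmetic.** Randomization is Day 1. For a completer first all-clear at Visit 6:

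- Protocol: 29 − 1 + 1 = 29.
- SAP as written: 137 − 1 + 1 = 137, or up to 144 − 1 + 1 = 144 with the window.

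The SAP value is the same whether clearance began on Day 8 or Day 137.

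**Kaplan-Meier artefact.** Suppose a proportion p of an arm clears, everyone completes, and Visit 13 dates are spread evenly over the eight days 137 to 144. One eighth of the arm leaves each day, so the risk set shrinks from 8/8 to 1/8, and the final survival estimate is S = ∏(1 − p/j) for j = 1 to 8. Estimated clearance, 1 − S, is:

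- p = 0.22: 1 − 0.527 = 47%
- p = 0.24: 1 − 0.495 = 51%
- p = 0.35: 1 − 0.344 = 66%

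A median can therefore appear to be reached when only 24% or 35% clear. If every Visit 13 fell exactly on Day 137, 1 − S would equal p and no median would be reached.

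**Power simulation.** Assumptions: 250 per arm; wart strata 45/20/12/23%, with less clearance when there are more warts; first clearance spread over Visits 3-13 as 2, 5, 8, 12, 13, 13, 12, 15, 9, 7 and 4%; 10% dropout, uniform over Visits 3-12; visit days drawn within the windows; 2,000 trials per scenario; stratified Breslow score test. Each cell shows protocol dating, then literal dating.

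| Ever clear, A-101 vs vehicle | Power | A-101 Kaplan-Meier clearance by Day 64 | A-101 median reached (share of runs) |
|---|---|---|---|
| 22% vs 10% | 0.951, 0.905 | 17.6%, 0.7% | 0-0.4%, 37% |
| 24% vs 14% | 0.794, 0.702 | 19.3%, 0.7% | 0-0.4%, 58% |
| 35% vs 20% | 0.962, 0.891 | 28.1%, 1.1% | 0-0.4%, 99.9% |

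With literal dating about 95% of events fall on Day 137 or later. The median event day among A-101 clearers moves from about 44 to 140.

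The extra ties are not the main cause. With the hypergeometric log-rank variance, power is 0.952 vs 0.916, 0.796 vs 0.724 and 0.963 vs 0.909. The losses are then 3.6, 7.2 and 5.4 points, against 4.6, 9.2 and 7.1 with Breslow, so ties explain 1 to 2 points of each.

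**A scenario with little loss.** At 16% vs 5% ever clear with uniform onset (600 runs, unstratified log-rank, 0-10% dropout), power is 98.0-99.0% with protocol dating and 97.5-98.5% with literal dating. Kaplan-Meier clearance on A-101 by Day 60 still drops from 11.5-11.8% to 0-0.6%.

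**Equal clearance, earlier onset on A-101.** With onset weights over Visits 3-13 of 3, 4, 4, 4, 3, 2, 2, 2, 1, 1, 1 (divided by 27) on A-101 and the reverse on vehicle, the rejection rate at 60% ever clear in both arms is 52-63% with protocol dating and 5-8% with literal dating. At 20% ever clear it is 5-9% and 4-8%, so little onset signal is detectable under either definition. With other assumed curves it is 28% vs 4% at 35% ever clear, and 11% vs 5% at 24%. These values depend on how much earlier A-101 is assumed to act.

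**Type I error** (4,000 null trials, Breslow score): 0.047 vs 0.045 at 14% clear, and 0.043 vs 0.036 at 20%.

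**RESPONSE.** At 24% vs 14% ever clear with recurrence in some clearers (700 runs), power is 0.78 for ever clear with protocol dating and 0.71 for ever clear with literal dating. For clear at last assessment it is 0.70 with protocol dating and 0.62 with literal dating. Each ambiguity costs about as much as the other.

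**Score vs Wald.** They disagree at 0.05 in 0.1-0.4% of runs.

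**The case against.** The strongest reply is that nobody would code it this way. The title and opening sentence of section 3.2.6 speak of time to clearance, the formula stands between two sentences about censoring, and protocol section 15.3 supplies the event date. That is a plausible account of the intention. But on that reading the SAP states no event time for an alpha-controlled test, while its code uses the one variable for both kinds of subject. The same correction is needed.

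Several qualifications do stand:

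- The power figures ignore the earlier gates. Requiring significance at Visits 10 and 13 as well gives about 0.85 vs 0.83, 0.65 vs 0.60 and 0.87 vs 0.82 in the three scenarios, which are smaller losses.
- In the equal-clearance case the Day 137 secondary test would normally fail first, so the effect there is on description more than on the confirmatory decision.
- The false medians depend on Visit 13 dates being spread over the window. They vanish if every visit is on its nominal day.
- The protocol wording on first achieving clearance largely settles RESPONSE as ever clear.
- The SAP cites protocol Version 4, while the protocol at hand is Version 5, so the silence of SAP section 3.6 proves little.
- SAP section 3.3 mentions a separate data-handling and programming document that was not available. It may hold the right derivation, but it would then contradict the formula printed in the SAP.

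**Conclusion.** The concern holds. As written, SAP section 3.2.6 contradicts protocol section 15.3. Read as a censoring rule only, it leaves the event time undefined.

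The certain consequence of literal coding is descriptive: completers' clearance dates move to Day 137-144, and the curves and medians no longer show onset. The loss of power is conditional. It is about 5 to 9 points for this test alone under the three main assumed scenarios, less once the earlier gates are applied, and close to nil at 16% vs 5%. All rates, onset patterns and dropout are assumptions.

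Nothing in the documents shows that the literal version was run. This should be fixed, but it does not threaten the main conclusions of the trial. The Score/Wald inconsistency is minor.

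**What to change.** Amend SAP section 3.2.6 as follows:

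- For RESPONSE = 1, DAYSFOL is the date of the first post-baseline visit with PWA = 0 on all treated warts, minus the randomization date, plus 1.
- For RESPONSE = 2, DAYSFOL is the date of the last wart assessment, minus the randomization date, plus 1. Keep the existing rule for subjects with no post-baseline assessment.
- Define RESPONSE = 1 as all treated warts clear at any post-baseline visit through Visit 13.
- Use the stratified log-rank (Score) p-value, which keeps to the protocol's log-rank test, and delete the Wald sentence. Breslow handling of ties can stay.
- Report a median only if it is reached.

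The cost is a few lines of text and code, with no new data. SAP section 3.6 records that Version 1.2 corrected a different section (3.2.4) after unblinding, so timing matters here too. List this change in 3.6 as a return to the protocol 15.3 rule and not as a new choice of analysis. If the literal version has already been run, show both results.
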